#### Sample Size Primary outcome

Our sample size estimation for the primary outcome is based on following assumptions:

- Significance level i.e.  $\alpha$  = 0.05 and 90% power
- Difference in the mean cotinine levels between control and intervention arms = 0.28 Standard Deviation = 1.38
- Intra-cluster correlation coefficient = 0.05
- Correlation between baseline covariate and outcome = 0.6

- 1. Effect size: We expect that the difference in the cotinine levels between children who are exposed to second-hand smoke and those who are not exposed is going to be more than 0.20. In addition, we expect that the difference in the cotinine levels between children who have different levels of exposure according to the smoking restrictions at home will also be more than 0.20. We believe that this is a clinically meaningful difference. We derive this difference from the research carried out by Ronchetti et al(18), who studied the relationship between cotinine levels among children and the place where the household members smoked while they were at home (specifically, if they smoked >4 cigarettes day-1 "at the dinner table" or "in the television room after dinner"). The smoking behaviour was classified in four categories accordingly. They found that the difference detected in the cotinine levels of children between different categories was greater than 0.20. Therefore, we are assuming that a shift of 0.20 in the cotinine levels in our study population will be of clinical significance; for example, this can be an important difference in the levels of exposure of children to SHS between adults smoking in one room only and not smoking inside the house. The calculations are based on an SD of 1.38 which would bring the detectable difference of 0.28 to 0.20 of a standard deviation. We think that 0.20 of a standard deviation is a relatively small effect to look for and in observational data is what we might expect to find.
- 2. Intra-cluster correlation coefficient is selected on the basis of what has been used for continuous outcomes in school based studies on tobacco, drug and alcohol use(49-51).
- 3. Size of the cluster (children in each school): We plan to recruit 40 children from each school with a positive cotinine test as baseline. We believe that this is achievable based on the following assumption. In an average primary school in Yorkshire & Humber, we expect three classes of 30 children each in a year which will give us a potential recruitment pool of 180 per school. Given that 40% children are expected to be exposed to SHS, we should have at least 100 participating children to give us a sample of at least 40 children with positive cotinine levels from both years.
- 4. Correlation between baseline covariate and outcome: We assume a relatively conservative correlation co-efficient between baseline and outcome covariate of 0.6. Cook et al(45) shows a correlation of greater than 0.8 between pre- and post salivary cotinine levels, which if holds for our study, will significantly increase its power.
- 5. Attrition rate: In terms of attrition, for the primary outcome, we assume a very low attrition (<5%) in line with previous trials we have undertaken in schools. For our sample size calculations we have been deliberately conservative in our estimates; if we had a 15% attrition, which we think unlikely, then our sample size would be 1700, which would give us power to show a 0.20 difference in effect size. Even if we end up following only 25 children in each school then based on SD of 1.38, d = 0.28, alpha = 0.05, ICC = 0.05 and corr = 0.6 the power will be around 0.85. Clearly, if attrition is lower (likely) and the ICC is lower (likely) and pre and post test correlation is higher (likely) then we would have more power to show a smaller difference.
- 6. Design effect: The design effect we used here is 2.95 (i.e.,  $[40-1] \times 0.05 + 1$ ).

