#### Smoke Free Homes – Theoretical framework

Negotiated goals: giving families a menu of options on how to reduce their children's exposure to tobacco smoke; letting them decide for themselves which of the options is achievable for the family, then signing the application at the bottom of the 'Promise' form before they posted back. Signing a contract: requiring parents to sign a 'contract' increases their commitment and the likelihood of their maintaining smoking restrictions in the home

Positive feedback: praising parents for the positive consequences of reducing their children's exposure to tobacco smoke increases self-esteem and self-efficacy in making changes in their lives. Immediate benefits: A basic principle of social marketing is that of 'exchange'; people expect to receive a benefit in exchange for giving up something.

Smoke Free Homes has been adapted in certain parts of the country (e.g. Salford, Nottingham, and Bristol). However, there have been limited reported evaluations. One report from Doncaster showed that 69% of households, signing up for smoking restrictions, promised a complete ban on smoking(35). A survey from Salford highlighted the finding that nearly all smokers who promised to keep their homes smoke-free were able to maintain their commitment in the following six-months(36). We carried out a feasibility study to; (a) test the appropriateness of SFH intervention; (b) refine and standardise SFH; and (c) assess potential methods for its evaluation in a deprived urban locality(37). We found that smoking in the presence of children had more than halved in households with at least one smoker; 42% at baseline, 20% at 6 months. The proportion of households being completely smoke free increased from 35% at baseline to 67% at 6 months. The need to evaluate interventions aimed at promoting smoke free homes is long established(32). Such evidence can belp in developing an effective policy and programme on SHS. SEH has a firm

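### The protocol argues that a 0.20 difference in cotinine level matters clinically but powers the trial for 0.28 (0.20 of an SD); the 90% power belongs to 0.28, and power at 0.20 is about 65%

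*Protocol*

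**What the plan says.** In the Protocol, section Sample Size Primary outcome, the assumptions list sets a 5% significance level and 90% power. Its other inputs are "Difference in the mean cotinine levels between control and intervention arms = 0.28 Standard Deviation = 1.38", "Intra-cluster correlation coefficient = 0.05" and "Correlation between baseline covariate and outcome = 0.6".

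Item 1 (Effect size) of that section is meant to justify the difference. It relies on a cited observational study that related children's cotinine to where household members smoked: "They found that the difference detected in the cotinine levels of children between different categories was greater than 0.20". From this it concludes: "Therefore, we are assuming that a shift of 0.20 in the cotinine levels in our study population will be of clinical significance". It then turns to the calculation: "The calculations are based on an SD of 1.38 which would bring the detectable difference of 0.28 to 0.20 of a standard deviation". It ends by defending a fifth of a standard deviation as a fairly small effect to look for.

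Item 5 (Attrition rate) says that 1700 children would still give power for a difference of 0.20, this time described as an effect size.

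No unit is given for 0.20, 0.28 or 1.38, and no reason is given for choosing 0.28.

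**The concern.** The number 0.20 does two jobs. In the clinical argument it is a difference in cotinine level. In the calculation it is a fraction of a standard deviation. If the figures share a scale, as the wording about cotinine levels implies, the powered difference is 0.28/0.20 = 1.4 times the difference called clinically significant. That difference is 0.20/1.38 = 0.145 SD, not 0.20 SD.

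The protocol leans on its power in three other places:

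- Ethical arrangements (Primary outcome and Sample size) calls under-powered trials unethical and describes this calculation as conservative with high power.
- The cost justification in the same chapter says NHS money could be redirected if the programme is found ineffective.
- The Control Group section offers the programme to control schools only if it is shown to be effective.

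A reader who attaches the 90% to the 0.20 shift would give a non-significant result more weight against the programme than the design supports.

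**Working it through.** **Inputs.** From Sample Size Primary outcome: difference 0.28, SD 1.38, ICC 0.05, correlation r = 0.6, α = 0.05, 40 cotinine-positive children per school, design effect 2.95. From Proposed sample size: 25 schools per arm, so 1000 cotinine-positive children per arm. Assumptions: the test is two-sided (sidedness is not stated), and 0.20, 0.28 and 1.38 are on one cotinine scale.

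**Standard error of the arm difference.**
- Design effect: 1 + 39 × 0.05 = 2.95.
- Effective n per arm: 1000 / 2.95 = 339.
- Residual SD after baseline adjustment: 1.38 × √(1 − 0.36) = 1.104.
- SE = 1.104 × √(2/339) = 0.0848.

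**Reproducing the protocol's figures.** Power = Φ(difference/SE − 1.96).
- At 0.28: Φ(3.302 − 1.96) = 91.0%. With a noncentral t on 48 degrees of freedom it is 89.9%. The protocol states 90%.
- At 25 children per school: design effect 1 + 24 × 0.05 = 2.2, effective n 625/2.2 = 284, SE 0.0926, power 85.6% (t: 84.2%). The protocol says "alpha = 0.05, ICC = 0.05 and corr = 0.6 the power will be around 0.85".

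Both figures reproduce, so this is evidently the method used. Ignoring the baseline correlation gives 75% at 0.28, and applying it only to within-school variance gives 80%. Neither matches.

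**The same design at other differences and sample sizes.**

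| Children per school | Power at 0.28, normal (t) | Power at 0.20, normal (t) |
|---|---|---|
| 40 (N = 2000) | 91.0% (89.9%) | 65.5% (63.7%) |
| 34 (N = 1700, 15% attrition) | 89.5% (88.2%) | 63.1% (61.3%) |
| 25 (N = 1250) | 85.6% (84.2%) | 57.9% (56.2%) |

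For 0.20 at N = 2000: Φ(0.20/0.0848 − 1.96) = Φ(0.40) = 65.5%.

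**Other quantities at N = 2000.**
- Difference detectable with 90% power: 3.2415 × 0.0848 = 0.275. With 80% power it is about 0.24.
- Exactly 0.20 SD is 0.20 × 1.38 = 0.276, where power is 90.2% (t: 89.1%).
- Expected 95% confidence interval half-width: 1.96 × 0.0848 = 0.17.
- Children needed for 90% power at 0.20: 1001 per arm before adjustment, × 2.95 × 0.64 = 1890 per arm, about 3780 in all. This is given for scale only.
- With r = 0.8: residual SD 1.38 × 0.6 = 0.828, SE 0.0636, power at 0.20 = 88%.

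**The case against.** The strongest defence has four parts.

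**The arithmetic is right and open.** The protocol lists 0.28 and 1.38 as its inputs, shows the conversion to 0.20 SD, and never says in terms that it has 90% power for a raw 0.20. All of this stands. A reader might infer that the 90% is miscalculated, but it reproduces at 0.28.

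**The differences are expected to exceed 0.20.** An assumed 0.28 is compatible with that, and powering for an expected effect above the smallest important one is a legitimate choice. But the protocol does not make that argument. It names 0.20 as clinically significant and links it to 0.28 only through the SD conversion.

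**The scale is unstated.** If 0.20 was always meant as a standardised effect, the design has about 90% power for it (1986 children needed against 2000 planned). This is possible, and it is why the 65% is conditional. In that case, however, the justification fails, because differences in cotinine level do not establish that 0.20 SD is clinically significant. The text needs correcting on either reading.

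**The inputs are called conservative.** Item 4 cites a correlation above 0.8. At 0.8, power for 0.20 is about 88%, so 65% is the planning-case figure and should be described as such.

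A stronger inference is also tempting. The 0.20 is a contrast between household categories, and the feasibility study reported: "The proportion of households being completely smoke free increased from 35% at baseline to 67% at 6 months". A reader might conclude that the arm difference will be only a fraction of 0.20, with very low power. The documents do not support a figure for that. The category gap is given only as a lower bound. The feasibility result is an uncontrolled before-and-after change in households of which 35% were already smoke free, whereas the primary analysis is of cotinine-positive children. Counting only complete bans also ignores the partial restrictions that the protocol accepts as an outcome.

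Finally, nothing in the protocol says that a null result will be read as proof of no effect. That risk comes from how the stated power may be used and is not a written error.

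**Conclusion.** The point holds as a mismatch between the difference that is justified and the difference that is powered. The 90% power is correct for 0.28 (0.20 SD) and for that only. At the 0.20 shift in cotinine level that the protocol calls clinically significant, the same planning inputs give about 64–65%. The figure is about 61–63% at N = 1700 and about 88% if the baseline correlation is 0.8.

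These figures assume a two-sided 5% test and a common scale for 0.20, 0.28 and 1.38. If 0.20 was intended as a standardised effect, the power claim stands but its clinical derivation does not. The severity is moderate: the design, endpoint and analysis are unaffected, but a power statement on which the ethical and funding arguments rest does not apply to the difference used to justify it.

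**What to change.** In Sample Size Primary outcome:

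1. State the unit of cotinine for 0.20, 0.28 and 1.38, and say whether 0.20 is a raw or a standardised difference.
2. Either report power at both values (about 90% for 0.28, i.e. 0.20 SD, and about 65% for a 0.20 shift, at r = 0.6), or justify 0.28 as the target in its own right and withdraw 0.20 as its basis.
3. Make the attrition item match: say whether the 0.20 that 1700 children can detect is in SD units or in cotinine level. Power is about 88–89% for 0.20 × 1.38 = 0.276 and about 61–63% for a raw 0.20.
4. Say, here or in the analysis plan, that a non-significant primary result will be read from its confidence interval (expected half-width about 0.17) against the named clinically significant difference, and not as evidence of no effect.

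The cost is protocol wording and a less favourable power statement at 0.20. No extra schools, children or measurements are needed.

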## **Ethical arrangements**

#### Rationale for carrying out this research

The Smoke Free Homes intervention has the potential to address a major public health issue i.e. second-hand smoke and its influence on the health of children. Given that this is now a problem largely among families with socio-economic disadvantage in the UK, the intervention also has a potential to address the health gap between rich and poor. However, there is no evidence for its effectiveness and cost-effectiveness that is based on objective outcome measure (cotinine test). Therefore these research questions address a priority need for deprived communities where both active and passive smoking are common.

Cost justification: If SFH is found effective in our study, it would provide justification to continue to expand this scheme which could potentially cost only 3 million pounds per year approximately at a national level. However, if found ineffective, the NHS would be able to divert this money to other cost-effective strategies. The low cost of intervention should not be a deterrent to invest in a robust evaluation. A cheap intervention, if found effective, is likely to be highly cost-effective. Developing robust evidence for the cost-effectiveness of a cheap intervention provides good value for money.

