#### Primary outcome and Sample size

We have selected salivary cotinine test as the primary outcome. Cotinine is the only objective measure that can detect the difference between active and passive smoking and therefore, be used as a valid measure in this study. Any alternative measure selected as primary outcome for this study will compromise its validity and invariably make the study less ethical. Providing the saliva sample for salivary cotinine testing is also not harmful to children.

Under-powered trials are considered unethical; therefore our sample size calculations are based on conservative estimates and high power. We have also taken account for the potential attrition.

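### The primary sample size uses 0.20 on two scales: a raw cotinine shift called clinically significant, and 0.20 of an SD (0.28 units), which is what the trial is sized for

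*Protocol*

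**What the plan says.** All the relevant text is in the protocol, under Statistical Considerations, Sample Size Primary outcome.

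- The list of assumptions sets alpha and power at "0.05 and 90% power" and gives "Difference in the mean cotinine levels between control and intervention arms = 0.28 Standard Deviation = 1.38", with an ICC of 0.05 and a baseline-outcome correlation of 0.6.
- Item 1 (Effect size) justifies a different figure. It expects cotinine to differ by more than 0.20 between exposed and unexposed children, and between levels of home restriction, and regards this as clinically meaningful. The source is an observational study that grouped households by where people smoked: "They found that the difference detected in the cotinine levels of children between different categories was greater than 0.20". The protocol concludes: "we are assuming that a shift of 0.20 in the cotinine levels in our study population will be of clinical significance".
- The next sentence changes scale: "The calculations are based on an SD of 1.38 which would bring the detectable difference of 0.28 to 0.20 of a standard deviation". The protocol adds that a fifth of an SD is fairly small and about what observational data would suggest.
- Item 5 (Attrition rate) says that 1,700 children would still give power for 0.20, here called an effect size, and that 25 children per school would give power of about 0.85 for a difference of 0.28.
- Under Ethical arrangements, the protocol states that "our sample size calculations are based on conservative estimates and high power".

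**The concern.** The number defended as clinically significant and the number entered in the calculation are not the same quantity. The first is written as a shift in cotinine levels and drawn from observed differences in cotinine. The second is 0.28 cotinine units, and it meets the first only because 0.28 divided by 1.38 is also about 0.20. Nothing in the section says why a raw 0.20 becomes a raw 0.28.

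This matters because item 1 is where the protocol justifies the target difference for the primary outcome. A reader who takes the clinical argument at face value will suppose that the trial is well powered for a shift of 0.20 in cotinine. If the true effect were that size, the chance of a significant result would be well below 90%, and a non-significant result would not by itself rule out a shift that the protocol calls clinically significant.

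**Working it through.** **Inputs**, from Proposed sample size and Sample Size Primary outcome: 25 schools per arm; 40 cotinine-positive children per school, so n = 1,000 per arm; SD 1.38; ICC 0.05; baseline-outcome correlation r = 0.6; alpha 0.05. The section does not say whether the test is two-sided. Two-sided is assumed here, and it reproduces the stated figures.

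**Method** (normal approximation)

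- Design effect: DE = 1 + (40 − 1) × 0.05 = 2.95, as stated in item 6.
- SD after baseline adjustment: 1.38 × √(1 − 0.6²) = 1.38 × 0.8 = 1.104.
- Standard error of the arm difference: SE = 1.104 × √(2 × 2.95 / 1,000) = 0.0848.
- Power = Φ(difference / SE − 1.96).

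**The plan's own figures**

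- Difference 0.28, 40 per school: 0.28 / 0.0848 = 3.30; power = Φ(1.34) = 91.0%. A t reference with 48 degrees of freedom gives 89.9%. The stated 90% is reproduced.
- Difference 0.28, 25 per school: DE = 1 + 24 × 0.05 = 2.20; n = 625 per arm; SE = 1.104 × √(2 × 2.20 / 625) = 0.0926; power = 85.6% (84.2% with t). The stated value of about 0.85 is reproduced.

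The method therefore agrees with the protocol's.

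**The two meanings of 0.20**

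- 0.20 SD in cotinine units: 0.20 × 1.38 = 0.276, or 0.28 rounded.
- 0.20 cotinine units in SD: 0.20 / 1.38 = 0.145 SD.

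**Power for a raw 0.20, same method**

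- 40 per school: 0.20 / 0.0848 = 2.36; power = Φ(0.40) = 65.5% (63.7% with t).
- 34 per school (the 1,700-child scenario): DE = 2.65; power = 63.1%. For 0.28 the same scenario gives 89.5%.
- 25 per school: power = 57.9%.
- Smallest difference detectable with 90% power at 40 per school: (1.960 + 1.282) × 0.0848 = 0.275.
- For scale only: 90% power at a raw 0.20 would need 641 per arm before clustering, so 641 × 2 × 2.95 ≈ 3,782 children in schools of 40, against 2,000 planned.

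**Sensitivity to r and ICC** (raw 0.20, 40 per school)

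| r | ICC 0.02 | ICC 0.03 | ICC 0.05 |
|---|---|---|---|
| 0.6 | 85.9% | 78.5% | 65.5% |
| 0.7 | 92.5% | 86.9% | 75.2% |
| 0.8 | 98.2% | 95.6% | 88.2% |

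If baseline adjustment removed only within-school variance, power for a raw 0.20 would be about 52%. That variant gives 80% for 0.28, so it does not reproduce the plan's figure, and it is not used for the conclusion.

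**The case against.** The strongest reply is that nothing has been miscalculated. The 90% is attached only to 0.28 with SD 1.38, and it reproduces. The difference of 0.28 is listed openly as the assumed difference between arms and converted openly to 0.20 SD, and 0.20 SD has a short rationale of its own. All of this stands. A reader might infer that the protocol claims 90% power for its clinically significant difference and really has 65%. The documents do not support that, because no power is claimed anywhere for a raw 0.20.

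Second, 0.20 may have been meant as a standardised effect throughout. The item is headed Effect size, the 0.20 in the clinical argument carries no unit, and the 1,700-child statement fits only the standardised reading (89.5%, against 63.1% for a raw 0.20). This is plausible, and what the cited study measured cannot be checked from the protocol. But on that reading the sentence about a shift in cotinine levels is misstated, and the cited differences, described as differences in cotinine levels, no longer support the target as written.

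Third, the cited differences are described as greater than 0.20, so 0.28 could be an expected effect. The protocol does not make that argument.

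Fourth, the inputs are described as conservative, and the protocol says that a lower ICC and a higher correlation would allow a smaller difference to be shown. That is fair: power for a raw 0.20 is 88% at r = 0.8 and 86% at ICC 0.02, and passes 90% under some joint improvements. The protocol does not quantify this for 0.20.

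Finally, a reader might infer that a non-significant result would lead directly to SFH losing its funding, since the ethics section says "if found ineffective, the NHS would be able to divert this money to other cost-effective strategies". That is a general cost argument. It does not equate non-significance with ineffectiveness.

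**Conclusion.** The point holds as an inconsistent target difference. The protocol justifies 0.20 in cotinine levels and sizes the trial for 0.28, joining the two only through 0.20 of an SD. On either reading the stated basis needs correcting: either the difference called clinically significant is not the one that was powered, or the sentence describing it as a shift in cotinine levels is wrong.

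At the planned inputs, power is about 91% for 0.28 units and about 65% for 0.20 units, so a true raw shift of 0.20 would be missed about one time in three (1 − 0.655 = 0.345). These figures rest on SD 1.38, ICC 0.05, r = 0.6, 40 children per school and a two-sided 5% test. With 40 per school and ICC 0.05, power for a raw 0.20 runs from about 65% to 88% as r goes from 0.6 to 0.8.

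**What to change.** State one target difference, with its unit, in Sample Size Primary outcome. Two forms would settle it:

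- **(a)** Declare 0.28 cotinine units (0.20 SD) as the target, correct the sentence that presents a shift of 0.20 in cotinine levels as the basis, and give a reason for 0.28.
- **(b)** Keep 0.20 cotinine units as the clinically significant shift, state that power for it is about 65% at the planned inputs (65–88% for r = 0.6–0.8 with 40 per school), and note that a non-significant result alone does not rule out that shift.

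The 1,700-child statement under Attrition rate should use the same unit. Neither form needs more recruitment or a change of design. The cost is a few sentences and, under (b), a less favourable stated power.
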